# Better treatment of type 2 diabetes and Binge Eating Disorder: Statistical Analysis Plan

## 1. Background

**Primary Objective:** The purpose of this pilot study is to evaluate the effect of cognitive behavioral therapy (CBT) on the number of weekly binge eating episodes among individuals with binge eating disorder (BED) and type 2 diabetes. As this is a pilot RCT, the focus will be on estimating effect sizes and identifying trends rather than testing hypotheses. The aim is to gather information on the potential effect of the intervention, which can inform the design of a future full-scale RCT.

## 2. Methods

**Study design:** This study is a non-blinded trial with a parallel design, where participants are randomized to either intervention (Cognitive Behavioral Therapy, CBT) or a waitlist control group. The aim of the design is to assess whether CBT is superior to the waitlist control group in terms of reducing weekly binge eating episodes. The intervention group will receive CBT over 16 weeks, while the control group will not receive treatment during the study period. The design allows for a direct comparison between the two groups to assess the effect of CBT, while also providing information on the feasibility of the intervention and potential effect sizes. This pilot study aims to gather data that can inform a potential future full-scale RCT.

## 3. Outcome Measures

### Primary Outcome:

- **Number of binge eating episodes per week:** The number of binge eating episodes per week will be assessed by changes in the average number of episodes, measured using the validated EDE-Q (Eating Disorder Examination Questionnaire). The questionnaire covers both symptoms and behaviors related to binge eating and eating disorders in general, and it is used as a standardized measure to assess both the frequency and intensity of binge eating episodes.

### Secondary Outcomes:

- **HbA1c:** Glycemic control will be measured by changes in HbA1c levels, assessed through blood tests, where HbA1c represents the average blood glucose over the past 2-3 months. HbA1c will be measured via blood tests at Odense University Hospital (OUH).
- **Time in Range (TiR) and Time Above Range (TAR) / Time Below Range (TBR):** Glycemic control will also be assessed using continuous glucose monitoring (CGM), which measures how long the participant's blood glucose stays within the desired range (TiR), as well as the time spent above and below the target range (TAR and TBR). The CGM sensor is blinded and is worn by participants for one week before being returned to OUH.
- **BED-Q:** Binge eating symptoms and behaviors will be assessed using the BED-Q (Binge Eating Disorder Questionnaire), a self-report tool that evaluates both the frequency and intensity of binge eating episodes.
- **EDE-Q:** Eating disorder symptoms will be further assessed with the EDE-Q, one of the most widely used tools in binge eating research.
- **MDI:** Depressive symptoms will be assessed using the Major Depression Inventory (MDI), a self-report questionnaire that measures symptoms of depression based on clinically defined criteria.

- **PAID-20:** The Problem Areas in Diabetes-20 will be used to assess diabetes-related distress, where participants report feelings and difficulties related to their diabetes treatment and management.
- **Lipid Profile:** Blood tests will be used to measure the lipid profile, including levels of total cholesterol, triglycerides, and HDL cholesterol.
- **BMI:** Weight and BMI will be measured via self-report on the EDE-Q, as weight will not be measured directly in the study. This choice has been made because weight loss is not the goal of the intervention, and to avoid influencing participants' expectations.
- **Blood Pressure:** Systolic and diastolic blood pressure will be measured using an automatic blood pressure monitor, providing information on changes in cardiovascular risk. Blood pressure will be measured using the MAM function (Multi-Measurement Mode) in calm clinical settings at OUH.

## 4. Statistical Analysis

### 4.1 Primary Analysis

Since this is a pilot study, the primary analyses will be exploratory and reported as descriptive statistics and inferential analyses. Changes in weekly binge eating episodes between groups will be estimated by:

- Mean and standard deviation for each group at both baseline and post-intervention
- Effect size calculated with Cohen's d to quantify the difference between groups
- 95% confidence intervals for the estimated effects
- Mixed-effects models: A mixed-effects model will be used to assess intraindividual changes in the number of binge episodes over time, accounting for both the intervention effect and individual differences. This model will allow time and group effects to be included as factors, and individual variation will also be considered. As this is a pilot study, the analysis will be exploratory and will not aim to test formal hypotheses with sufficient statistical power.
- Given the potential risk of reduced statistical power due to the limited sample size, alternative statistical methods, such as paired t-tests or Wilcoxon signed-rank tests, will be considered if necessary.

As there is insufficient power to draw definitive conclusions about the intervention's effect, the focus will be on identifying trends and possible effect sizes that can inform a future full-scale RCT.

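### SAP section 4.1 names only time and group as mixed-model factors and does not say which term or contrast is the CBT effect; read literally, its group coefficient estimates half that effect

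*SAP*

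**What the plan says.** Section 2 of the SAP gives the comparative aim: to "assess whether CBT is superior to the waitlist control group in terms of reducing weekly binge eating episodes". Section 4.1 opens its list of primary analyses with "Changes in weekly binge eating episodes between groups will be estimated by". The list contains:

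- descriptive statistics: "Mean and standard deviation for each group at both baseline and post-intervention";
- Cohen's d "to quantify the difference between groups";
- "95% confidence intervals for the estimated effects";
- a mixed model, introduced as follows: "A mixed-effects model will be used to assess intraindividual changes in the number of binge episodes over time, accounting for both the intervention effect".

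The only sentence on the content of that model is "This model will allow time and group effects to be included as factors, and individual variation will also be considered". Section 4.1 ends by giving the purpose of the results as identifying trends and "possible effect sizes that can inform a future full-scale RCT".

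The section mentions an intervention effect but links it to no coefficient or contrast. The fallback methods it lists (paired t-test, signed-rank test) are within-person tests, so they do not show which between-group contrast is meant. Sections 4.2 and 4.3 do not settle it either.

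**The concern.** In a randomised comparison with a baseline and a post-intervention measurement, the treatment effect is the group difference after treatment, either as a difference in change or adjusted for baseline. In a mixed model it is carried by the group-by-time term or an equivalent contrast. It is not carried by the group main effect of a model without that term, which averages over both visits, including the one before treatment began.

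The two factors that section 4.1 names are exactly those of a main-effects model. One analyst could fit them as listed and report the group coefficient. Another could infer the interaction from the lead-in and report that. The two estimates would differ about two-fold, and their confidence intervals would refer to different quantities. Because the pilot does no formal testing, the estimate and its interval are its main product, and they are meant to feed the design of a full-scale trial.

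**Working it through.** **Inputs.** From the SAP: two randomised parallel arms (section 2), and means and SDs at baseline and post-intervention (section 4.1). The SAP gives no sample size, SD, correlation or expected effect, so there is no figure to reproduce. Assumed for illustration: n = 20 per arm (range 10 to 30), SD σ = 2 episodes per week at both visits, baseline–post correlation ρ = 0.5 (range 0.3 to 0.7), true CBT effect δ = −2 (1 SD), and smaller effects of 0.5 SD and 0.3 SD.

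**Step 1: what the group main effect estimates.** With complete data at two visits and a random intercept, the group coefficient of a time + group model is the difference between arms in person means:

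group coefficient = ½(D_baseline + D_post).

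Randomisation makes the expected D_baseline 0, and the expected D_post is δ. The expectation is therefore ½(0 + δ) = δ/2. For a linear model this is algebra: it does not depend on σ, ρ, n or normality. The time coefficient is the average change over both arms. With a waitlist change of −0.5 and a CBT change of −2.5 it is (−0.5 − 2.5)/2 = −1.5.

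Simulated mixed models with 4,000 per arm and δ = −2 agree at ρ = 0.3, 0.5 and 0.7. The additive group coefficient was −0.99 to −1.00, the group-by-time term about −1.99, and the group-by-time term with a common baseline mean about −1.99. With 10% to 30% of follow-up missing and multiple imputation from group and baseline, at 20 per arm, the additive coefficient was still −0.98 to −1.01.

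**Step 2: standard errors at σ = 2, n = 20, ρ = 0.5.**

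- Additive group coefficient: σ√((1+ρ)/n) = √(4 × 1.5/20) = √0.30 = 0.55
- Change (group-by-time) contrast: σ√(4(1−ρ)/n) = √(4 × 2/20) = √0.40 = 0.63
- Baseline-adjusted contrast: σ√(2(1−ρ²)/n) = √(4 × 1.5/20) = √0.30 = 0.55

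**Step 3: coverage of the true effect by the additive CI.** The interval is centred |δ|/2 away from δ. In units of its SE the shift is 1/0.55 = 1.83 at 1 SD, 0.5/0.55 = 0.91 at 0.5 SD and 0.3/0.55 = 0.55 at 0.3 SD. With the t distribution and normal data:

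| True effect | 20 per arm, ρ = 0.5 | 10–30 per arm, ρ = 0.3–0.7 |
|---|---|---|
| 1 SD | 0.57 | 0.34–0.79 |
| 0.5 SD | 0.86 | 0.78–0.91 |
| 0.3 SD | 0.92 | 0.89–0.94 |

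At 1 SD, the change contrast and the baseline-adjusted contrast both covered the true effect in 95% of simulated trials.

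**Step 4: gain from baseline adjustment over the change contrast.** The SE ratio is √((1+ρ)/2) = 0.81, 0.87 and 0.92 at ρ = 0.3, 0.5 and 0.7. These are reductions of 19%, 13% and 8%. In simulation at 20 per arm the reductions were 18%, 12% and 6%.

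**The case against.** The strongest reply is that the text around the model sentence points to the right analysis. The lead-in speaks of between-group changes, the model is meant to assess within-person change, and section 3 defines the outcome through changes. A main-effects model forces equal change in both arms, so it cannot deliver that target. The model sentence is also permissive and excludes nothing. This stands. A reader might infer that the SAP commits to a main-effects-only model, and the document does not support that.

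A reader might also infer that the pilot would pass on a halved effect size unnoticed. That is not supported either. The visit means and SDs, and a Cohen's d calculated from them, are unaffected and would expose a discrepant coefficient. What remains ambiguous is the model estimate and its interval.

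Third, poor coverage is not a general result. The figure of 0.57 rests on an assumed 1 SD effect; at 0.3 SD coverage is close to nominal. Only the factor of one half is free of such assumptions.

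Fourth, naming the plain group-by-time term would be enough to remove the bias. That is correct; baseline adjustment is an additional gain in precision.

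Exploratory status does not answer the point, because estimating the effect is what the pilot is for. Nor is the choice of contrast something that a SAP ordinarily leaves to the protocol: section 4.1 sets out to describe the model and stops short of saying what it estimates.

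**Conclusion.** The concern holds as under-specification that should be fixed before analysis. Section 4.1 names two factors and no treatment contrast. Fitting just those factors gives a group coefficient and 95% CI centred on half the CBT effect. That result needs only a linear model, one baseline and one post-intervention visit, and randomised arms. The coverage and SE figures also rest on normal data with equal SDs and on assumed values of n, ρ and δ, none of which the SAP supplies; a weekly episode count may depart from them.

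Whether Cohen's d refers to change or to post-intervention values is a separate and minor gap. With equal SDs, a d on change scores is 1/√(2(1−ρ)) = 0.85, 1.00 and 1.29 times a d on post-intervention scores at ρ = 0.3, 0.5 and 0.7.

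**What to change.** Add to section 4.1 that the CBT effect is the baseline-adjusted difference between groups in weekly binge episodes post-intervention, reported with its 95% CI. Estimate it in one of two ways:

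- a mixed model with time and group-by-time and a common baseline mean for the two arms; or
- ANCOVA of the post-intervention value on group and baseline.

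If the authors prefer the plain group-by-time change contrast, naming it would also remove the bias, at the cost of the larger SE shown above. Optionally, tie Cohen's d to the same contrast and state which SD is its denominator.

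The cost is one or two sentences and no new data. The common baseline mean relies only on the randomisation already planned.

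### The paired tests named as a low-power fallback measure before-after change only and cannot estimate the effect of CBT against waitlist

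*SAP*

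**What the plan says.** Section 2 (Methods) describes an open-label, two-arm parallel trial that randomises people to CBT or to a waitlist. It gives the purpose as a comparison of arms: "The aim of the design is to assess whether CBT is superior to the waitlist control group in terms of reducing weekly binge eating episodes". It adds: "The design allows for a direct comparison between the two groups to assess the effect of CBT".

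Section 4.1 (Primary Analysis) opens its list of methods with "Changes in weekly binge eating episodes between groups will be estimated by". The list contains:

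- means and SDs by group at baseline and post-intervention;
- "Effect size calculated with Cohen's d to quantify the difference between groups";
- 95% confidence intervals;
- a mixed-effects model, of which the SAP says "This model will allow time and group effects to be included as factors, and individual variation will also be considered".

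The last bullet cites the risk of low power in a small sample and says that "alternative statistical methods, such as paired t-tests or Wilcoxon signed-rank tests, will be considered if necessary". It names no between-arm alternative and does not say what would make a switch necessary.

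**The concern.** The fallback answers a different question from the one the list is meant to answer. A paired t-test or signed-rank test on baseline and post-intervention values asks whether participants changed. The design asks whether CBT participants changed more than waitlist participants.

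The reason given for the switch adds to the problem. Low power for the randomised comparison is not cured by testing something else. A paired test in the CBT arm looks more powerful only because it treats the waitlist change as known and equal to zero.

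If a paired result in the CBT arm were read as the effect of CBT, it would include everything that also changes on the waitlist, such as natural course and regression to the mean. It could look positive with no benefit from CBT. The pilot's stated use is to supply effect sizes for a full-scale trial, so an estimate inflated in this way could mislead that planning.

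**Working it through.** The SAP states no sample size, SD, expected change or power, so there is no figure to reproduce. The main point follows from what each test estimates. The arithmetic only illustrates its size.

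**Step 1: what each method estimates.** Let c be the mean change on the waitlist and τ the extra change due to CBT. Mean change is then c + τ in the CBT arm and c in the waitlist arm.

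| Method | Quantity estimated |
|---|---|
| Paired test, CBT arm | c + τ |
| Paired test, waitlist arm | c |
| Paired test, arms pooled, equal numbers | (c + τ + c)/2 = c + τ/2 |
| Between-arm comparison of change | (c + τ) − c = τ |

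Only the last row isolates τ. The table is written in means for the t-test. The signed-rank test likewise uses only the within-person differences and has no group term. Section 2 describes no matching or crossover that would create pairs across arms.

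**Step 2: assumptions for the illustration (none from the SAP).** Change scores are normal with SD 1. There are n = 10, 20 or 30 per arm. Tests are two-sided at 5%. The common improvement c is 0.3, 0.5 or 0.8 SD of change.

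**Step 3: no CBT effect (τ = 0), both arms improve by c.** The paired t-test in the CBT arm has n − 1 degrees of freedom and noncentrality c√n. At c = 0.5 this is:

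- n = 10: 0.5 × √10 = 1.581, 9 df
- n = 20: 0.5 × √20 = 2.236, 19 df
- n = 30: 0.5 × √30 = 2.739, 29 df

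Proportion of trials with p<0.05:

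| Test | n = 10 | n = 20 | n = 30 |
|---|---|---|---|
| Paired t, CBT arm, c = 0.3 | 0.136 | 0.247 | 0.355 |
| Paired t, CBT arm, c = 0.5 | 0.293 | 0.565 | 0.754 |
| Paired t, CBT arm, c = 0.8 | 0.616 | 0.924 | 0.988 |
| Signed-rank, CBT arm, c = 0.5 (simulated) | 0.295 | 0.539 | 0.735 |
| Between-arm t on change, c = 0.5 (simulated) | 0.052 | 0.049 | 0.047 |
| Between-arm rank-sum, c = 0.5 (simulated) | 0.045 | 0.049 | 0.046 |

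The paired t rows come from the noncentral t distribution. The signed-rank row uses 6,000 simulated trials and the between-arm rows 20,000.

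Testing each arm separately and comparing the p-values does not help. With p for a significant paired t-test in one arm, a significant CBT arm beside a non-significant waitlist arm has probability p(1 − p). At c = 0.5 this is 0.293 × 0.707 = 0.21, 0.565 × 0.435 = 0.25 and 0.754 × 0.246 = 0.19 for n = 10, 20 and 30.

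**Step 4: where the apparent power gain comes from.** Let CBT change by 0.5 SD and the waitlist by 0. The paired test in the CBT arm has noncentrality 0.5√n. The between-arm t-test has 0.5√(n/2) on 2n − 2 df. At n = 20 these are 2.236 and 0.5 × √10 = 1.581.

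| Test | n = 10 | n = 20 | n = 30 |
|---|---|---|---|
| Paired t, CBT arm | 0.293 | 0.565 | 0.754 |
| Between-arm t | 0.185 | 0.338 | 0.478 |

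The paired row equals the c = 0.5 row in Step 3, where CBT had no effect. The test cannot distinguish a true CBT effect from an equal improvement in everyone.

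**The case against.** The strongest reply is that the between-arm estimate is never given up. Cohen's d between groups and the 95% confidence intervals are separate, unconditional items, and an interval for a between-group effect is itself inference. The fallback wording is permissive and its tests are only examples. Nothing says a paired result would replace the mixed model or be read as the CBT effect. The SAP also disclaims formal hypothesis testing and states no significance level, so error rates at p<0.05 describe a verdict the pilot does not plan to give. The illustration assumes normal change scores although the outcome is an episode count, and its range of 14% to 99% does not measure the risk in this trial.

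Much of this stands as a limit on the consequence. The flaw lies in the fallback and not in the whole primary analysis, and the percentages apply only if a paired p-value is misread. It does not make the named tests suitable. Section 4.1 also promises inferential analyses, and section 2 speaks of superiority.

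A softer reading takes the paired tests as a simple substitute for the within-person part of the mixed model, which the SAP does mention. That does not fit a bullet offering them as alternatives because of low power, in a list introduced as estimating between-group change. The group means and SDs in the same list are not contrasts either, but they are description for both arms and are not offered in place of the comparison.

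**Conclusion.** The concern holds. As written, the named fallback cannot estimate the CBT-versus-waitlist effect and does not restore power for it. This rests on the parallel design and on the definition of the tests, not on any assumed number.

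The size is conditional. Under the assumptions above, with no CBT effect and a CBT-arm paired p-value taken as the treatment effect, the false-positive rate would be 29% to 75% at a common improvement of 0.5 SD. It would be 14% to 36% at 0.3 SD and 62% to 99% at 0.8 SD, against about 5% for a between-arm test. With a real CBT change of 0.5 SD and none on the waitlist, the gap at 20 per arm (56% against 34%) reflects the assumption of zero waitlist change and not better use of the data.

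Because the between-group effect size with its interval stays in the plan, this is a point that should be fixed and not one that invalidates the analysis.

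**What to change.** Replace the paired tests in the last bullet of section 4.1 with one prespecified between-arm small-sample method. Two suitable choices are:

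- the baseline-adjusted difference at post-intervention with a permutation or bootstrap 95% confidence interval; or
- a rank-sum test on change scores with a Hodges-Lehmann estimate and its confidence interval.

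Either report it beside the mixed model in all cases, or tie its use to a stated criterion other than low power, such as non-convergence of the mixed model. Paired within-arm results may stay if they are labelled as description only.

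The cost is one sentence of SAP wording. No further data or participants are needed.

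### The effect size meant to inform the full-scale RCT is a Cohen's d with no small-sample correction and no word on how its imprecision will be used, and the feasibility information promised in Section 2 has no outcome or analysis behind it

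*SAP*

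**What the plan says.** Section 1 makes effect estimation the purpose of the pilot: "The aim is to gather information on the potential effect of the intervention, which can inform the design of a future full-scale RCT". Section 4.1 repeats this ("the focus will be on identifying trends and possible effect sizes that can inform a future full-scale RCT") and names the measure: "Effect size calculated with Cohen's d to quantify the difference between groups". It mentions neither a small-sample correction nor the SD used as standardiser.

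The same list in 4.1 also plans "Mean and standard deviation for each group at both baseline and post-intervention", "95% confidence intervals for the estimated effects" and a mixed-effects model. It gives no number of participants, only a caution: "Given the potential risk of reduced statistical power due to the limited sample size". It concedes that power is too low for firm conclusions.

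Section 2 says the design compares the groups "while also providing information on the feasibility of the intervention and potential effect sizes". Section 3 lists binge eating episodes as the primary outcome, then glycaemic, questionnaire, lipid, BMI and blood pressure outcomes. Section 4 covers the primary analysis, sensitivity and secondary analyses, and missing data. Neither section contains a measure of recruitment, retention, session attendance or data completeness.

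**The concern.** What the pilot passes on to the next trial is its main product, and two parts of it are poorly fixed.

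First, Cohen's d overstates the population effect on average when samples are small, and a standard correction exists. A sample size varies with the inverse square of the effect, so the relative error in d roughly doubles in the sample size. Sampling error in d is also large in a small pilot, and the SAP does not say how planners should allow for it.

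Second, retention, attendance and completeness are quantities that a later trial needs and that a pilot can supply. The SAP announces feasibility information, but a team that follows its outcome and analysis sections would produce none. Attendance that is not recorded during the trial may be hard to recover afterwards.

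**Working it through.** The SAP gives no sample size, SD, power or expected effect, so there is no figure of its own to reproduce. The arithmetic below is an illustration.

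**Assumptions:** equal arms of 10, 20 or 30; normal outcome; pooled SD as standardiser; observed d of 0.5, with 0.8 as a second value; next trial at 80% power and two-sided 5%.

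**Step 1: bias.** With df = 2n - 2, the Hedges factor is J = Γ(df/2)·√(2/df) / Γ((df - 1)/2), close to 1 - 3/(4df - 1). At 20 per arm the approximation is 1 - 3/151 = 0.980. The relative upward bias of d is 1/J - 1, and g = J·d. The next trial's size per arm is 2(1.96 + 0.8416)²/d² = 15.70/d², rounded up; at d = 0.5 this is 15.70/0.25 = 62.8, so 63.

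| n per arm | J | Bias of d | g for d = 0.5 | Next trial per arm, from d | from g |
|---|---|---|---|---|---|
| 10 | 0.9576 | 4.4% | 0.48 | 63 | 69 |
| 20 | 0.9801 | 2.0% | 0.49 | 63 | 66 |
| 30 | 0.9870 | 1.3% | 0.49 | 63 | 65 |

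**Step 2: imprecision.** Take t = d·√(n/2) and find the noncentrality values that put t at the 97.5th and 2.5th percentiles of the noncentral t distribution. Divide them by √(n/2) to get the 95% CI for the population effect.

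| n per arm | 95% CI at d = 0.5 | Next trial per arm at upper limit | at lower limit |
|---|---|---|---|
| 10 | -0.40 to 1.38 | 9 | none (negative) |
| 20 | -0.13 to 1.13 | 13 | none (negative) |
| 30 | -0.02 to 1.01 | 16 | none (negative) |

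A t-based calculation adds one per arm: 64 at d = 0.5, and 10, 14 and 17 at the upper limits. For an observed d of 0.8 at 20 per arm the CI is 0.15 to 1.44, which corresponds to 699 down to 8 per arm (from unrounded limits).

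**Step 3: which matters more.** At 20 per arm and d = 0.5 the bias is about 0.5 × 0.02 = 0.01. The half-width of the CI is (1.13 + 0.13)/2 = 0.63. Simulation of 200,000 pilots per setting shows the same ordering. Suppose, hypothetically, that the next trial were sized on the point estimate alone. The share of pilots leading to real power below 50% would be:

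| True d | n per arm | Sized on d | Sized on g |
|---|---|---|---|
| 0.5 | 10 | 32.1% | 29.8% |
| 0.5 | 20 | 25.2% | 23.8% |
| 0.5 | 30 | 20.5% | 19.5% |
| 0.8 | 10 | 25.1% | 22.1% |
| 0.8 | 20 | 16.3% | 14.7% |
| 0.8 | 30 | 11.3% | 10.3% |

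The correction removes the bias and leaves most of the planning risk in place.

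**Step 4: what such a pilot estimates better.** At 20 per arm (38 df) the chi-square interval puts the SD between 0.82 and 1.29 times its estimate. Retention of 32 out of 40 has an exact 95% CI of 0.64 to 0.91; limits for each arm separately would be wider.

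**Step 5: feasibility.** Set against the promise in Section 2, Section 3 has no feasibility outcome and 4.1 no feasibility estimate. The nearest items are the check in 4.2 on departures from the inclusion criteria and the multiple imputation in 4.2 and 4.3. Neither estimates retention, attendance or completeness.

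**The case against.** The strongest reply is that the SAP is already cautious. It plans confidence intervals, group means and SDs and a mixed model, so the imprecision of d will be visible and d is not the only output. The raw difference can be computed from the planned group means. It calls its effect sizes possible or potential and concedes low power. All of this stands, and it limits the point to what the SAP leaves unnamed: the correction, the raw difference with its CI, and how the estimates will be used.

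A reader might infer that the next trial will be sized on the pilot's point estimate, or that the missing correction would mis-size it. The documents support neither. The SAP says only that results can inform a later trial, and Step 3 shows that the correction changes the risk very little. How that trial is sized is properly a matter for its own protocol.

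A reader might also infer that multiple imputation conceals how many participants were lost. It does not: imputing values leaves the count of missing values known. The narrower observation is that no planned output reports that count by arm.

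On feasibility, the protocol is not at hand and may define such measures, so their absence from the SAP would not be a fault by itself. What remains is an internal mismatch: Section 2 announces an output that Sections 3 and 4 neither contain nor refer elsewhere.

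**Conclusion.** The point holds in a limited form. The SAP's named effect size is biased upward by about 4%, 2% and 1% at 10, 20 and 30 per arm. The bias is small but avoidable at almost no cost. Imprecision is the main planning risk; it will be visible in the planned CIs, but the SAP gives no guidance on its use. The feasibility mismatch depends on no assumption and can be read directly from the text.

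The numerical results rest on assumed arm sizes and effects, because the SAP states neither, and on normality. Weekly episode counts are likely to be skewed, so the figures show orders of magnitude only. They do not show that the next trial will be mis-sized, nor that the pilot as a whole lacks feasibility measures.

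**What to change.** 1. In Section 4.1, replace Cohen's d with Hedges' g and its 95% CI. Report beside it the between-group difference in episodes per week with its 95% CI.
2. In Section 4.1, add one sentence: any use of these results for planning will take account of the confidence interval and the raw-scale SD, not the point estimate alone.
3. In Sections 3 and 4, add retention and completeness of the primary outcome by arm, both reported before imputation with exact 95% CIs, and the number of CBT sessions attended. If the protocol already defines these, a cross-reference is enough.

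The cost is some wording and a few lines of analysis. Retention and completeness come from data the trial produces anyway; attendance needs a session record. The downside is a slightly smaller headline effect size.
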